**Table 4. Schedule of Assessments – SCREENING**

Obtain Informed Consent	X
Review Inclusion/Exclusion Criteria	X
Medical History	X
Physical Examination (PE)	X
12 Lead ECG	X
ECOG Performance Status	X
Vital Signs	X
Clinical laboratory tests	
Complete Blood Count (CBC)	X
Serum chemistry	X
Pregnancy test (if applicable)	X
Urinalysis (dipstick)	X
Concomitant medication review	X
Tumour imaging	X

**10.4.2 Phase Ia (Run-In) Arm Schedule of Procedures**

The procedures in this arm of the Study are summarized in Table 5.

**Table 5. Schedule of Assessments -Phase Ia (Run-In) Arm**

Study Day	1	8	15	21
Physical Examination (PE)	X	X	X	
12 Lead ECG 	X	X	X	
Vital Signs 	X	X	X	
Clinical laboratory tests				
Complete Blood Count (CBC) 	X	X	X	
Serum chemistry 	X	X	X	
Urinalysis (dipstick) 	X	X	X	
Concomitant medication review	X	X	X	X
PK /Biomarker sampling	X 	X 	X 	
Urine collection 	X	X	X	
Adverse events/toxicity assessment	X	X	X	X
Dispense study drug	X		X	

 ECG conducted 1-hour post NOX66 dosing on Days 1 and 8; any time Day 15.

 Vital signs = blood pressure, pulse, respiratory rate and body temperature.

 See Section 6.4 for list of blood tests.

 Plasma for PK analysis to be collected (Day 1) at t = 0, 30 min, 1 hr and 2 hr post-dosing.

 Plasma for PK analysis to be collected (Day 8) at t = 0, 1 hr and 2 hr post-dosing.

 Plasma for PK analysis to be collected (Day 15) at 24 hr post-dosing.

 24-hr urine sample to be collected starting from the time of NOX66 dosing on Day 1.

 Return study drug for in-clinic administration

 Phone call to confirm dose level and continuation to Phase1b.

### 10.4.3 Phase Ib (Combination) Arm and End of Study Schedule of Procedures

The procedures in this arm of the Study are summarized in Table 6.

**Table 6. Schedule of Assessments -Phase Ib (Combination) Arm**

Study Day 	Commencing Treatment Cycle				Second and subsequent treatment cycles				End of Study 
	1 	2 	7 	15	1	2	7	15	
Physical Examination (PE)		X	X	X	X	X	X	X	X
12 Lead ECG 		X	X			X			X
ECOG Performance Status		X	X	X			X	X	X
Vital Signs 		X	X	X	X	X	X	X	X
Clinical laboratory tests									
Complete Blood Count (CBC)		X	X	X	X		X	X	X
Serum chemistry		X	X	X	X		X	X	X
Pregnancy test (if applicable)									X
Concomitant medication review		X	X	X	X	X	X	X	X
Tumour imaging 									
PK/Biomarker sampling 			X				X		
Adverse events/toxicity assessment		X	X	X	X	X	X	X	X
Dispense study drug	X				X				

 There is ± 1-day window allowable for each clinic visit.

 Day 1: Commence NOX66 treatment

 Day 2: Return study drug for in-clinic administration; Carboplatin treatment 1-hour post-NOX66 administration;

 Day 7: Return study drug for in-clinic administration and conclude NOX66 treatment

 ECG 1-hour post-NOX66 administration

 Vital signs: = weight, blood pressure, pulse, respiratory rate and body temperature.

 Tumor burden to be assessed by CT/MRI according to the Investigator's judgement at minimum every 12 weeks.

Confirm objective response in 4 weeks.

 See Section 10.4.6 - 10.4.7 for the timing of collection of blood and urine for PK and blood for biomarker analyses.

 +28 – 33 days after last dose of Carboplatin treatment

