### 8.2 INCLUSION CRITERIA

Patients must fulfill all of the following inclusion criteria to be eligible to enroll into the study:

1. Provision of informed consent.
2. Male or female  $\geq 18$  years of age.
3. Histologic or cytologic confirmed locally advanced or metastatic cancer that has no standard therapeutic alternatives.
4. At least 1 measurable lesion by CT/MRI scan.
5. ECOG Performance status 0-1 (Appendix A).
6. A minimum life expectancy of 12 weeks.
7. Adequate bone marrow, hepatic and renal function as evidenced by:
  - Absolute neutrophil count (ANC)  $> 1.5 \times 10^9/L$
  - Platelet count  $> 100 \times 10^9/L$
  - Hemoglobin  $> 9.0$  g/dL
  - Serum bilirubin  $< 1.5 \times$  ULN
  - AST/ALT (SGOT/SGPT)  $< 2.5 \times$  ULN for the reference laboratory or  $< 5 \times$  ULN in the presence of liver metastases
  - Serum creatinine  $< 1.5 \times$  ULN
8. Female patients who are known to be capable of conception should have a negative serum pregnancy test (beta-human chorionic gonadotropin ( $\beta$ -hCG)) within 1 week of starting the study.
9. All potentially fertile patients will agree to use an effective form of contraception during the study and for 90 days following the last dose of NOX66 (an effective form of contraception is defined as an oral contraceptive or a double barrier method).
10. At least 4 weeks must have elapsed prior to commencement of NOX66 treatment since prior chemotherapy, investigational drug or biologic therapy and any toxicity associated with these treatments has recovered to  $\leq$  NCI-CTCAE Grade 1.

11. At least 21 days must have elapsed prior to Day 1 Cycle 1 since radiotherapy (limited palliative radiation is allowed > 2 weeks), immunotherapy or following major surgery and any surgical incision should be completely healed.

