## 9.4 TREATMENT DOSE MODIFICATIONS

There will be no dose modification of idronoxil on the basis of body weight except where the patient exceeds 100 kg body weight in which case the dose of idronoxil may be increased (up to double) at the discretion of the investigator.

If a patient experiences a  $\geq$  Grade 3 adverse event assessed as causally associated with idronoxil during the Run-In phase, the patient should be withdrawn from the study. If a patient experiences a  $\geq$  Grade 3 adverse event assessed as causally associated with idronoxil during the Combination Arm, the patient may continue on idronoxil treatment at their assigned dose provided:

- 1) the adverse event has resolved to no more than Grade 2 by the time of commencement of the next Treatment Cycle;
- 2) a treatment break of  $> 2$  weeks due to an unresolved adverse event will require discontinuation of study treatment.

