ECG parameters at each time point will be presented by patient and by time point. The results will be presented by dose cohort.

**Efficacy Analysis:** Tumor measurements will be assessed by radiologic methods at baseline and at subsequent intervals at the discretion of the Investigator but not greater than every 12 weeks. Efficacy variables will include overall response, duration of objective response, time to progression, progression free survival (PFS), and overall survival. Response and progression will be assessed according to RECIST (Eisenhauer et al., 2009).

Continuous data will be summarized by descriptive statistics, including sample size, mean, standard deviation, median and range. Categorical data will be summarized by the number and percentage of patients. For the time-to-event endpoints, Kaplan-Meier estimates will be plotted.

Median event time and the associated 95% confidence interval will be provided. In addition, all the data will be presented in the data listings. The final statistical analysis for the study will be scheduled when all patients have completed at least one course of study drug administration, have reached a study endpoint (e.g., DLT or disease progression), and have at least 28 days of follow-up.

Best overall response, duration of objective response (complete response or partial response), PFS, time to progression and overall survival will be listed for all patients with measurable or evaluable disease by dose level. Any patient with insufficient data to determine response will be classified as a non-responder. Among patients with an objective response, duration of objective response will be defined as the time from the initial CR or PR to the time of disease progression or death on study, whichever occurs first. For patients who are alive and have not experienced disease progression on study, duration of objective response will be censored at the day of the last tumor assessment. Time to disease progression is defined as the time from the first day of study drug administration (Day 1) to disease recurrence or progression on study. Progression free survival (PFS) is defined as the time from the first day of study drug administration (Day 1) to disease recurrence or progression, or death on study. Patients who are alive and disease progression-free will be censored at the date of last disease evaluation.

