## 15.2 RESPONSIBILITIES FOR REPORTING

Investigators and the Sponsor are required by regulatory agencies worldwide to report adverse events which involve patients being administered a pharmaceutical product.

All serious adverse events (SAE) occurring from the signing of informed consent until 30 calendar days after last study treatment, whether related to drug or not, must be reported to the Medical Monitor and appropriate Sponsor contact person within 24 hours of first knowledge of the experience using the appropriate study SAE Report Form. SAEs are to be followed until resolution or stabilisation (with autopsy report if applicable).

Deaths and other SAEs occurring > 30 calendar days after last study treatment that are deemed 'possibly' or 'probably' related to the study treatment must be reported as SAEs on the SAE Report Form within 1 day of first knowledge of the event by the treating physician or research personnel (with an autopsy report if available).

Deaths occurring > 30 calendar days after study trial treatment and not attributed to study treatment (e.g., disease progression) need not be reported as SAEs, but simply captured on the appropriate CRF.

The investigative sites will send the SAE report to the Sponsor's Medical Monitor via fax or e-mail using the contact information below.

Primary Contact  Medical Monitor: [name] [name]	[contact] [contact] Email#: [contact]
Alternate Contact  Study Manager: [name]	[contact]; [contact] [contact] Email: [contact]

Pharmacovigilance (DATAPHARM Australia) Manager: [name]	[contact]; [contact] Email: [contact]
---	---

Transmission of the SAE Report Form should be confirmed by the site personnel submitting the report.

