#### **15.2.4 Pregnancy**

If a study patient or a patient partner becomes pregnant while enrolled in the trial, a Pregnancy Form should be completed and faxed to the Sponsor expeditiously, irrespective of whether or not it meets the criteria for expedited reporting. Abortions (spontaneous, accidental, or therapeutic) must also be reported to the Sponsor.

Congenital anomalies/birth defects always meet SAE criteria, and should therefore be expeditiously reported as an SAE, using the previously described process for SAE reporting. The previous completed Pregnancy Form must be updated to reflect the outcome of the pregnancy.

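### End of Study is timed from the last carboplatin dose, so run-in-only patients have no defined closing visit and, on planned dosing, the visit comes before the 30-day SAE window closes

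*Protocol*

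**What the plan says.** - **Protocol Table 6, footnote 9 (Phase Ib), repeated in Table 9 (Phase IIa).** End of Study takes place "28 – 33 days after last dose of Carboplatin treatment". In both tables it carries a physical examination, ECG, ECOG status, vital signs, blood count, chemistry, a pregnancy test where applicable, and adverse event review.
- **Protocol Table 5 (run-in).** There is no End of Study column. Examination, ECG and laboratory tests are last scheduled on Day 15. Day 21 has only adverse event and medication review, and its footnote describes it as a "Phone call to confirm dose level and continuation to Phase1b".
- **Protocol 15.2.** SAEs are reportable, related or not, when "occurring from the signing of informed consent until 30 calendar days after last study treatment".
- **Protocol 10.1.1 and 10.1.2.** Run-in NOX66 is given on Days 1-14 of 21. In each 28-day combination cycle NOX66 is given on Days 1-7 and carboplatin on Day 2.
- **Protocol Table 6, footnote 1.** "There is ± 1-day window allowable for each clinic visit".
- **Protocol 13.2 and SAP 3.1.** One dose of idronoxil is enough to enter the safety population, so run-in-only patients are counted in it.
- **Related time limits.** Protocol 13.2 lets the final analysis be scheduled once, among other conditions, patients "and have at least 28 days of follow-up". Inclusion criterion 9 requires contraception "for 90 days following the last dose of NOX66", while 15.2.4 asks for a report if a patient or partner "becomes pregnant while enrolled in the trial".

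**The concern.** Two clocks are in use. The closing visit runs from carboplatin, and the SAE window runs from the last study treatment of either kind. On the planned schedule the last treatment is NOX66, five days after carboplatin (7 - 2 = 5). For a patient who leaves in the run-in, the first clock never starts.

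Run-in exits are foreseen. Protocol 10.1.2 only offers the combination, and 8.4 lists DLT, an intolerable related event and withdrawal of consent as reasons to leave. Protocol 9.4 says that a patient with a related event of Grade 3 or higher "during the Run-In phase, the patient should be withdrawn from the study".

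Tolerability and the adverse event profile are primary objectives. Protocol 13.2 gives treatment-emergent events a start but no end date, and the 30-day window in 15.2 is written for SAEs. How completely non-serious late events and the recovery of abnormal laboratory values are recorded therefore depends largely on when the patient is last seen.

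**Working it through.** The documents give no derived figure to reproduce. The check is day arithmetic.

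**Inputs.** Carboplatin Day 2 and last NOX66 Day 7 (10.1.2, Table 8); visit 28-33 days after carboplatin (Tables 6 and 9); SAE window 30 days after last study treatment (15.2); run-in last dose Day 14 and last contact Day 21 (10.1.1, Table 5).

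**Combination cycles, planned dosing**
- Visit day = 2 + 28 to 2 + 33 = cycle Days 30-35.
- Days after last study treatment = 30 - 7 to 35 - 7 = 23-28.
- SAE window closes = 7 + 30 = Day 37.
- Visit is early by 37 - 35 to 37 - 30 = 2-7 days.
- With ±1 day the visit falls on Days 29-36, which is 22-29 days after last treatment and 1-8 days early.

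Counted from carboplatin, day 30 is Day 32, which lies inside Days 30-35. This is why the 28-33 day range looks as if it covers the window.

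**Combination cycles, NOX66 stopped early in the last cycle** (no ±1 day)

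| Last NOX66 day | Visit, days after last treatment | SAE window closes |
|---|---|---|
| 7 | 23-28 | Day 37 |
| 6 | 24-29 | Day 36 |
| 5 | 25-30 | Day 35 |
| 4 | 26-31 | Day 34 |
| 3 | 27-32 | Day 33 |
| 2 | 28-33 | Day 32 |

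The visit can reach day 30 only if NOX66 stopped by Day 5, or by Day 6 with the ±1-day window (23-30 days).

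**Run-in only**
- Last dose Day 14: window closes 14 + 30 = Day 44. The last tests are 15 - 14 = 1 day after the last dose and the call is 21 - 14 = 7 days after. The time without scheduled contact is 44 - 21 = 23 days.
- Last dose Day 8, for illustration: window closes Day 38, and 38 - 21 = 17 days.

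**Pregnancy.** Measured from the last NOX66 dose on planned dosing, the closing visit leaves 90 - 28 = 62 to 90 - 23 = 67 days of the contraception period after it.

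**The case against.** The strongest reply is that safety reporting does not depend on a visit. Under 15.2 all SAEs to day 30 are reportable within 24 hours and are followed to resolution or stabilisation. Section 15.2.1 repeats the follow-up, 15.2.2 covers treatment-related events after discontinuation, and 8.4 requires withdrawn patients to be followed to establish whether a related event was the reason. All of this stands. A reader might infer that SAEs will be lost and that the safety tables will understate toxicity. The documents show only that a scheduled opportunity to detect events is missing. What remains is that 8.4 sets no date, examination or laboratory test, and the last-visit instruction in 15.2.2 asks patients only about SAEs thought to be related, which is narrower than 15.2.

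A reader might also infer that the missing visit weakens the DLT and MTD determination. It does not. Section 10.1.4 judges both within the first 21-day cycle, and Table 5 assesses toxicity on Days 1, 8, 15 and 21. A visit near Day 44 would change no escalation decision.

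Nor is every combination patient seen too early, as the table of early stops shows. If carboplatin is withheld in the final cycle and NOX66 is given, the footnote read literally puts the visit on Days 2-7 of that cycle (30 - 28 to 35 - 28). No site is likely to hold a closing visit during treatment, so this shows a poor anchor and should not be read as a likely event.

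It can be argued that run-in patients are meant to have the visit, because 10.2.2 places a pregnancy test at End of Study without limiting it to one arm. Even so, the visit would have no date.

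Finally, the number of run-in exits is uncertain. Protocol 9.4 withdraws run-in patients with related toxicity of Grade 3 or higher, whereas the synopsis and the text after Table 3 reduce the dose and remove the patient only if toxicity persists. Those passages must be reconciled separately. Exits occur under either.

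**Conclusion.** The point holds as a gap in scheduled follow-up. Run-in-only patients have no defined closing visit, and up to 23 days pass without scheduled contact before the SAE window closes if dosing reaches Day 14 (fewer if it stops earlier). Combination patients who take NOX66 through Day 7 are seen 2-7 days before the window closes, or 1-8 if the ±1-day allowance also applies to this visit. For those who stop NOX66 early in the last cycle, the visit may reach day 30.

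The figures assume dosing on the scheduled days and that last study treatment in 15.2 means the later of the two drugs. The documents do not say how many patients will leave in the run-in.

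Two further points are secondary. The 28-day minimum in 13.2 has no stated starting point, so it is shorter than the SAE window but cannot be shown to fall inside it. Section 15.2.4 does not say when enrolment ends, so it is unclear whether a pregnancy in the later part of the 90-day contraception period is reportable. It would go too far to say that such pregnancies are excluded.

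**What to change.** 1. In Tables 6 and 9, time End of Study from the last dose of NOX66 or carboplatin, whichever is later, and no earlier than 30 days after it. With a ±1-day window the target should be day 31 or later, so that the earliest permitted visit is day 30.
2. Add the same visit to Table 5 for any patient who does not enter Phase Ib.
3. In 13.2, state when the minimum follow-up starts and make it cover the 30-day SAE window.
4. In 15.2.4, align the pregnancy reporting period with the 90-day contraception period.
5. Separately, reconcile 9.4 with the synopsis and 10.1.1 on run-in toxicity above Grade 2.

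The cost is a protocol amendment, one routine visit for each run-in-only patient, and a later pregnancy enquiry. For a patient who finishes NOX66 on Day 7, a day-31 target falls on cycle Day 38 (7 + 31), which is 3-8 days later than the present Days 30-35. No new type of procedure is needed, and items 1 to 4 change no dose or treatment rule.

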### 10.4.4 NOX66 Dosing Schedules

**Table 7. Schedule of NOX66 Treatment in Phase Ia (Run-In) Arm**

Study Day	1-7	8-14	15-21
NOX66	X	X	Rest

**Table 8. Schedule of NOX66 Treatment in Phase Ib (Combination) Arm per Cycle**

Study Day	1	2	3-7	8-28
NOX66	X	X	X	Rest
Carboplatin	Rest	X	Rest	Rest

### 10.4.5 Phase IIa Arm Schedule of Procedures

The procedures in this arm of the Study are summarized in Table 9.

**Table 9. Schedule of Assessments - Phase IIa Arm**

Study Day 	Commencing Treatment Cycle				Second and subsequent treatment cycles				End of Study 
	1 	2 	7 	15	1	2	7	15	
Physical Examination (PE)	X	X	X	X	X	X	X	X	X
12 Lead ECG 			X			X			X
ECOG Performance Status	X		X	X			X	X	X
Vital Signs 	X	X	X	X	X	X	X	X	X
Clinical laboratory tests									
Complete Blood Count (CBC)	X		X	X	X		X	X	X
Serum chemistry	X		X	X	X		X	X	X
Pregnancy test (if applicable)									X
Concomitant medication review	X	X	X	X	X	X	X	X	X
Tumour imaging 									
Biomarker sampling 			X				X		
Adverse events/toxicity assessment	X	X	X	X	X	X	X	X	X
Dispense study drug	X				X				

 There is ± 1-day window allowable for each clinic visit.

 Day 1: Commence NOX66 treatment

 Day 2: Carboplatin treatment 1-hour post-NOX66 administration

 Day 7: Conclude NOX66 treatment

 ECG 1-hour post-NOX66 administration

 Vital signs: = weight, blood pressure, pulse, respiratory rate and body temperature.

 Tumor burden to be assessed by CT/MRI according to the Investigator's judgement at minimum every 12 weeks. Confirm objective response in 4 weeks.

 See Section 10.4.7 for the timing of collection of blood for biomarker analyses.

 +28 – 33 days after last dose of Carboplatin treatment

### 10.4.6 Pharmacokinetic Analysis

**Phase Ia (Run-In) Arm:** All patients in the Phase Ia (Run-In) Arm will have plasma and urine analyses conducted over the 21-day treatment cycle.

Blood to be collected on Days 1, 8 and 15 at the following times (Table 10):

**Table 10. PK Blood Sampling Schedule for Phase Ia (Run-In) Arm**

Day	Sampling time in relation to NOX66 administration
1	t = 0 (pre-dose), then 0.5, 1, and 2 hr post-dose*
8	t = 0 (pre-dose), then 1 hr and 2 hr post-dose*
15	t = 24 hr post-dose

\*Post dosing sampling may be taken following administration of the first suppository for Cohort 2 patients.

24-hour urine will be collected on Days 1, 8 and 15, commencing from the time of NOX66 administration on those days and returned at following visit day.

**Phase Ib (Combination) Arm:** Blood samples to be collected from all patients on Day 7 of each Treatment Cycle at t = 1hour post-dosing. Post dosing sampling may be taken following administration of the first suppository for Cohort 2 patients.

### 10.4.7 Biomarker Analysis

Blood for biomarker analysis will be collected at the following times:

**Phase Ia (Run-In):** sample collected from all patients on Days 1, 8 and 15 as follows:

**Table 11. Biomarker Blood Sampling Schedule for Phase Ia (Run-In) Arm**

Day	Sampling time in relation to NOX66 administration
1	t = 0 (pre-dose), then 1 hr post-dose*
8	t = 1 hr post-dose*
15	t = 24 hr post-dose

\*Post dosing sampling may be taken following administration of the first suppository for Cohort 2 patients.

**Phase Ib:** sample collected from all patients on Day 7 of each cycle, 1hour post dose. Post dosing sampling may be taken following administration of the first suppository for Cohort 2 patients.

## **11 METHODS OF ASSIGNMENT OF INTERVENTION**

### **11.1 ALLOCATION OF TREATMENT**

NOX66-001A is a Phase I open-label, non-randomized, dose-escalation study of idronoxil in suppository form. Patients will be consented, screened and identified as eligible for the study by the Investigator at each site. Eligible patients will be allocated a number for identification on the electronic Case Report Form (eCRF) and for patient tracking purposes. The patients' ID will be determined by a one-digit site number, plus a two-digit patient number, which will be allocated chronologically and will be site specific e.g. first patient at site 1 will be number: 1-01, then sequentially 1-02, 1-03 etc. Likewise, site 2 first patient would be 2-01, 2-02, etc. Study numbers will only be used once and will not be reallocated to any other patient during the study.

Patients should begin protocol treatment within 72 hours of enrollment. Issues that would cause treatment delays longer than 72 hours should be discussed with the Sponsor. If a patient does not proceed to receive protocol therapy following enrollment, the patient's study enrollment may be cancelled and the patient will be considered a screen failure. The Sponsor should be notified of screen failures as soon as possible.

Sites will be notified by the Sponsor's Medical Monitor that enrollment to a cohort has been suspended so no further patients are recruited, until it is determined that either additional patients will be enrolled at the existing dose level or that enrollment to the next cohort may commence.

